8.7.2 Sensitivity Efficacy Analysis

8.7.2.1 Sensitivity Analyses for Absolute Change in Lesion Count

The first sensitivity analysis for absolute change in lesion count will use a repeated measures ANCOVA, with treatment, analysis center, visit (i.e., Weeks 2, 4 and 8), and treatment group by visit interaction as independent factors and a covariate of Baseline lesion count. In this analysis, data from all post-baseline visits will be included with no imputation for missing data.

The second sensitivity analysis will use the model based multiple imputation method to impute missing data for the absolute change in lesion counts at Week 12. The multiple imputation will involve 3 principal tasks:

1. Missing values will be filled in 5 times to generate 5 complete data sets. The imputation model used will be an ANCOVA with factors of treatment group and analysis center, and a covariate of Baseline lesion count (i.e., the imputation model will be the same as the analysis model).

Syntax:

```
proc mi data=datain out=dataout seed=&seed. nimpute=5 <options>;  
  class trtpn sitegr1;  
  var trtpn baseline sitegr1 week12;  
  monotone logistic (sitegr1=trtpn baseline);  
  monotone reg (week12=trtpn baseline sitegr1);  
run;
```

2. Each complete data set will be analyzed with an ANCOVA with factors of treatment group, and analysis center, and a covariate of Baseline lesion count. Appropriate modifications will be made should the analysis be based on a non-parametric method.
3. Results from these analyses will be combined into a single inference.

One random seed will be needed to impute the inflammatory lesion counts. The following random seed has been pre-specified by using a random number generator:

Inflammatory Lesion Count Seed=1543491304

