8. STATISTICAL AND ANALYTICAL PLANS

8.1 General Methodology

All statistical processing will be performed using SAS® version 9.3 or later unless otherwise stated. Statistical significance will be based on two-tailed tests of the null hypothesis resulting in p-values of 0.05 or less. These methods are intended to analyze the results of the study.

The primary method of handling missing efficacy data will be based on estimation using the method of Markov Chain Monte Carlo (MCMC) imputation. This method provides robust estimation when the pattern of missingness is arbitrary. Additionally, the estimation will be done for each treatment group separately so that the pattern of missingness for one group does not influence the estimation of missing data for another group. Groups of complete datasets following the estimation will be concatenated to form analysis datasets for the comparative analyses and subsequent imputation result inference with SAS PROC MIANALYZE.

Descriptive statistics will also be derived from the multiply imputed datasets.

Additionally, a model-based multiple imputation process will be used as a sensitivity analysis to the MCMC imputation. Finally, the absolute change in lesion count will be analyzed using a repeated measures analysis of covariance (ANCOVA) for lesion count data and a repeated measures logistic regression model (generalized estimating equations) for the dichotomized IGA.

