8.7.2.2 Sensitivity Analyses for IGA

The first sensitivity analysis for the dichotomized IGA success will use a repeated measures logistic regression model (generalized estimating equations), with dichotomized IGA success as the dependent variable and treatment, analysis center, visit (i.e., Weeks 2, 4 and 8), and treatment group by visit interaction as independent factors. In this analysis, data from all post-baseline visits will be included with no imputation for missing data.

The second sensitivity analysis will use the model based multiple imputation method to impute missing data for the dichotomized IGA data. The multiple imputation will involve 3 principal tasks:

1. Missing values will be filled in 5 times to generate 5 complete data sets. The imputation model used logistic regression with factors of treatment group and analysis center (i.e., the imputation model will be the same as the analysis model).

Syntax:

```
proc mi data=datain out=dataout seed=&seed. nimpute=5 <options>;  
  class trtpn sitegr1 diiga;  
  var trtpn sitegr1 diiga;  
  monotone logistic (sitegr1=trtpn);  
  monotone logistic (diiga=trtpn sitegr1);  
run;
```

2. Each complete data set will be analyzed with a logistic regression a factors of treatment group and analysis center.
3. Results from these analyses will be combined into a single inference.

One random seed will be needed to impute IGA. The following random seed has been pre-specified by using a random number generator:

IGA Seed= 184392230

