10. CHANGES IN THE PLANNED ANALYSES

There are no changes in the conduct of the study, but there are minor changes to the planned analyses.

Due to feedback received, the primary efficacy analysis was adjusted back to the original analysis. The modification to only use the non-parametric version as described in v4 of the protocol was not accepted by the agency. The original approach uses an ANCOVA analysis with the terms for treatment, analysis center, and Baseline count (and treatment-by-center interaction if the term is significant at 0.10). If the two-sided p-value for the skewness test is significant at 0.01, then the rank-transformed data will be used instead of nominal values. The original approach was accepted by the agency.

The pooling analysis described in the protocol is updated in the statistical analysis plan (SAP) to reflect the intended analysis. The protocol discusses pooling sites with five or fewer subjects enrolled in each treatment arm. Taking into consideration the randomization ratio, the SAP requires ten subjects in the active treatment arm and five subjects in the vehicle group.

As part of the pooling analysis, the treatment effect within investigational site must be investigated. The protocol states the site main effect will be examined by using a one-way analysis of variance (for lesion count variables) or a logistic regression analysis (for dichotomized IGA) with a factor of site. The SAP instead explains site will be incorporated into the primary analysis models. Change from Baseline in lesion counts will be analyzed with an ANCOVA (unranked or ranked) with factors of treatment group, investigational site and treatment group by investigational site interaction, and the respective Baseline lesion count variable as a covariate. The dichotomized primary endpoint will be analyzed with a logistic regression with factors of treatment group, investigational site and the interaction term of treatment group by investigational site.

The protocol describes repeated measures sensitivity analyses for the primary efficacy endpoints. Treatment group, analysis center and visit are listed as factors for the repeated measures analyses. In addition to these factors, the SAP includes a factor of treatment group by visit interaction.

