Baseline IGA	Moderate		Severe	
	E-BPO 5% Cream (N=xxx)	Vehicle Cream (N=xxx)	E-BPO 5% Cream (N=xxx)	Vehicle Cream (N=xxx)
Inflammatory Lesion Count – Absolute Change from Baseline				
n	xxx	xxx	xxx	xxx
Mean	xx.x	xx.x	xx.x	xx.x
SD	xx.xx	xx.xx	xx.xx	xx.xx
Median	xx.x	xx.x	xx.x	xx.x
Min. to Max.	xx to xx	xx to xx	xx to xx	xx to xx
Achieving Clear or Almost Clear				
Success	xx.x%	xx.x%	xx.x%	xx.x%
Failure	xx.x%	xx.x%	xx.x%	xx.x%

^a Ethnicities of Not Reported and Unknown are not included.

Note: Multiple imputation (MCMC) used to impute missing values. Summary statistics represent average values, obtained from averaging the summary statistics generated from each imputed dataset. Negative absolute change values represent decrease from Baseline.

SOURCE: USERNAME\SPONSOR\PROJECT\JOBNAME (DATE, TIME)

Table 14.2.5.1: Sensitivity Analysis of Primary Endpoints: Absolute Change from Baseline in Inflammatory Lesion Count and Dichotomized IGA Success at Week 12
(Intent-to-Treat Population)
(Page 1 of 2)

	E-BPO 5% Cream (N=xxx)	Vehicle Cream (N=xxx)	Skewness P-Value	Treatment P-Value
Inflammatory Lesion Count – Absolute Change from Baseline				
LSMean ^a	xx.x	xx.x	x.xxx ^b	x.xxx ^a
LSSD ^a	xx.xx	xx.xx		x.xxx ^c
Achieving Clear or Almost Clear				
Success	xx.x%	xx.x%	N/A	x.xxx ^d
Failure	xx.x%	xx.x%		

^a Least squares means, standard deviations and treatment p-value from a repeated measures analysis of covariance with factors of treatment group, analysis center, visit and treatment group by visit interaction, and Baseline lesion count as a covariate. Negative least squares means values represent decrease from Baseline.

^b Skewness test based on methods presented by J.H. Zar (1984).

^c P-value from a ranked repeated measures analysis of covariance with factors of treatment group, analysis center, visit and treatment group by visit interaction, and Baseline lesion count as a covariate.

^d P-value from a repeated measures logistic regression with factors of treatment group, analysis center, visit and treatment group by visit interaction.

SOURCE: USERNAME\SPONSOR\PROJECT\JOBNAME (DATE, TIME)

Table 14.2.5.1: Sensitivity Analysis of Primary Endpoints: Absolute Change from Baseline in Inflammatory Lesion Count and Dichotomized IGA Success at Week 12
(Intent-to-Treat Population)
(Page 2 of 2)

	E-BPO 5% Cream (N=xxx)	Vehicle Cream (N=xxx)	Skewness P-Value	Treatment P-Value

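### The repeated-measures sensitivity analyses omit Week 12 from the visit list and name no Week 12 contrast, although they are reported as Week 12 results

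*SAP*

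**What the plan says.** SAP 8.7.2.1 describes the first sensitivity analysis of lesion-count change as a "repeated measures ANCOVA, with treatment, analysis center, visit (i.e., Weeks 2, 4 and 8), and treatment group by visit interaction as independent factors", with baseline count as covariate. It continues: "In this analysis, data from all post-baseline visits will be included with no imputation for missing data". SAP 8.7.2.2 sets up the GEE logistic model for IGA success in the same way, with "treatment, analysis center, visit (i.e., Weeks 2, 4 and 8), and treatment group by visit interaction as independent factors", and follows it with the same statement about which data enter. Protocol 19.4.8.1 and 19.4.8.2 carry the same three-visit list, without the interaction.

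The results go to Table 14.2.5.1, titled "Sensitivity Analysis of Primary Endpoints: Absolute Change from Baseline in Inflammatory Lesion Count and Dichotomized IGA Success at Week 12". Page 1 of that shell has one LSMean per arm and one treatment p-value for lesions (plus a ranked p-value), and success percentages with one p-value for IGA. Footnote a begins "Least squares means, standard deviations and treatment p-value from a repeated measures analysis of covariance with factors of treatment group, analysis center, visit" and goes on to the interaction and the covariate. Footnote c describes the ranked version in the same terms. Footnote d reads "P-value from a repeated measures logistic regression with factors of treatment group, analysis center, visit and treatment group by visit interaction".

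SAP section 10 records one change to these models relative to the protocol: "In addition to these factors, the SAP includes a factor of treatment group by visit interaction". It does not mention the visit list or the contrast to be reported.

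**The concern.** Both co-primary endpoints are at Week 12, and Week 12 is the only scheduled post-baseline efficacy visit missing from the list. A model whose visit factor has levels 2, 4 and 8 cannot estimate a Week 12 effect. A model with all four visits can, but only if someone asks for it. Once treatment-by-visit is in the model, the plain treatment effect is either an average over visits or the effect at a reference visit, depending on coding.

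These two models are the only planned inferential analyses of the co-primaries that use no imputation. The ITT primary analysis uses MCMC multiple imputation, the per-protocol analysis uses LOCF or baseline values, and the second sensitivity analysis uses model-based multiple imputation. They would therefore show whether the Week 12 finding depends on imputed values. If the printed number is not the Week 12 effect, neither agreement nor disagreement with the primary result can be interpreted. While the rule is open, the choice of number could be made after unblinding.

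**Working it through.** **Step 1: set the statements side by side.** No sample size, power or alpha figure of the plan is involved, so there is none to reproduce.

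| Place | What it implies about visits |
|---|---|
| SAP 8.7.2.1 and 8.7.2.2, visit factor; protocol 19.4.8.1 and 19.4.8.2 | Weeks 2, 4, 8 |
| SAP 8.7.2.1 and 8.7.2.2, next sentence | all post-baseline visits, which SAP 8.7 gives as Weeks 2, 4, 8 and 12 |
| Table 14.2.5.1, title | Week 12 |
| Table 14.2.5.1, page 1, footnotes a, c, d | model factors only, no visit named |
| SAP 7.1.1, co-primary endpoints | Week 12 |

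Read literally, the first row conflicts with the second and third. Adding Week 12 to the first row removes that conflict, but the fourth row still does not say which treatment effect is printed.

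**Step 2: what the unnamed treatment effect can be.** In a simulated data set (2000 active, 1000 vehicle, four visits, effects building up as 25/50/80/100% of the Week 12 effect), a model with treatment, visit and treatment-by-visit gave visit-specific differences of -1.55, -3.41, -5.01 and -6.41. From that one model:

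- The sum-coded treatment main effect was -4.09, which equals the visit average.
- The reference-coded treatment coefficient was -1.55 with Week 2 as reference.
- The reference-coded treatment coefficient was -6.41 with Week 12 as reference.

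**Step 3: how far an average could sit from Week 12.** Inputs from SAP section 9:

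- Lesions: -14.1 versus -7.4, so the Week 12 difference is 6.7.
- IGA success: 53.3% versus 20.0%, so the log odds ratio is ln(0.533/0.467) - ln(0.20/0.80) = 1.5185 and the odds ratio is exp(1.5185) = 4.57.

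The documents give no effects at Weeks 2, 4 or 8, so the fractions f2, f4 and f8 of the Week 12 effect are assumptions.

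- Average without Week 12 = (f2 + f4 + f8)/3.
- Average with Week 12 = (f2 + f4 + f8 + 1)/4.
- Lesion difference = average × 6.7.
- IGA odds ratio = exp(average × 1.5185), with the same fractions applied on the log-odds scale.

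For the 25/50/80% pattern: (0.25 + 0.50 + 0.80)/3 = 0.517 and (0.25 + 0.50 + 0.80 + 1)/4 = 0.638.

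| Assumed % at Weeks 2/4/8 | Average without / with Week 12 | Lesions without / with | Odds ratio without / with |
|---|---|---|---|
| 100/100/100 | 1.000 / 1.000 | 6.70 / 6.70 | 4.57 / 4.57 |
| 40/60/90 | 0.633 / 0.725 | 4.24 / 4.86 | 2.62 / 3.01 |
| 25/50/80 | 0.517 / 0.638 | 3.46 / 4.27 | 2.19 / 2.63 |
| 10/30/70 | 0.367 / 0.525 | 2.46 / 3.52 | 1.75 / 2.22 |
| 5/20/60 | 0.283 / 0.463 | 1.90 / 3.10 | 1.54 / 2.02 |
| 80/110/110 | 1.000 / 1.000 | 6.70 / 6.70 | 4.57 / 4.57 |
| 120/130/110 | 1.200 / 1.150 | 8.04 / 7.70 | 6.19 / 5.73 |

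Other time courses lead to the same conclusion. A linear build-up gives 2.61 lesions without Week 12 and 3.63 with it. An effect that appears only after Week 8 gives 0.00 and 1.68.

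**The case against.** The best defence is that the intent can be recovered. The all-visits sentence, the table title, the endpoint definitions and the added interaction all point to Week 12, and only the parenthesis points away, so it looks like a slip carried over from the protocol. A variant reads Weeks 2, 4 and 8 as the three non-reference levels with Week 12 as reference, in which case the treatment coefficient is the Week 12 effect. The slip is plausible, but correcting it does not settle the contrast. The reference-level reading does not fit a parenthesis introduced by i.e., and no coding is stated. Even under that coding, a plain treatment LSMean still averages over visits. A table title does not define what is estimated.

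The per-protocol analysis is also offered as a Week 12 check with largely observed values, since SAP 8.4.4 requires attendance at Week 12 within the window. It is a useful check, but it uses a selected subset. Discontinuations for a related adverse event or documented lack of effect are kept and set to baseline, with LOCF otherwise (SAP 8.1.5).

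Three parts of the objection stand:

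- SAP 8.1 says that "a model-based multiple imputation process will be used as a sensitivity analysis to the MCMC imputation", so the repeated-measures models are not the plan's named check on the primary imputation. For lesions, the named check does target Week 12.
- The time courses are assumed and show only that the gap can be large, absent or reversed. The simulation shows how coding behaves and says nothing about this trial.
- Rank-scale LSMeans have no place in the shell; only the ranked contrast p-value needs to be shown. The SAP also leaves the covariance structure and the GEE working correlation open, a separate gap that this correction does not close.

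The SAP is to be finalized before unblinding and statistical staff stay blinded until lock, which makes a late choice less likely. It does not supply the missing rule.

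**Conclusion.** The concern holds, with high confidence on the text. The stated visit factor contradicts both the next sentence and the table title, and following it literally cannot give a Week 12 effect. Adding Week 12 alone would leave a treatment result that may average over visits.

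From a flat pattern to the 5/20/60% pattern, the average is 46 to 100% of the Week 12 effect with Week 12 included (3.1 to 6.7 lesions; odds ratio 2.02 to 4.57) and 28 to 100% without it (1.9 to 6.7 lesions; odds ratio 1.54 to 4.57). An early peak exceeds 100%. These ranges rest on assumed time courses applied to the planned Week 12 effects, so neither the size nor the direction of the gap is known in advance.

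The reach is limited to the first sensitivity analysis of each co-primary. The co-primary tests, alpha, gatekeeping and sample size are untouched. It should be corrected, but the primary inference does not depend on it.

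**What to change.** Before unblinding:

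1. In SAP 8.7.2.1 and 8.7.2.2, define visit as Weeks 2, 4, 8 and 12.
2. In SAP 8.7.2.1, pre-specify the Week 12 LSMeans and the Week 12 treatment contrast from the treatment-by-visit term. For the ranked model, pre-specify the Week 12 contrast p-value.
3. In SAP 8.7.2.2, pre-specify the Week 12 treatment contrast (odds ratio) from the GEE.
4. On page 1 of Table 14.2.5.1, amend footnotes a, c and d to say that the results are the Week 12 contrast. Page 2, for the model-based imputation, stays as it is.
5. Record the correction to protocol 19.4.8.1 and 19.4.8.2 in SAP section 10.

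The cost is wording in two SAP sections, one line in section 10, one contrast statement per model and three footnotes on one table page. No new data are needed.

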8.7.2.2 Sensitivity Analyses for IGA

The first sensitivity analysis for the dichotomized IGA success will use a repeated measures logistic regression model (generalized estimating equations), with dichotomized IGA success as the dependent variable and treatment, analysis center, visit (i.e., Weeks 2, 4 and 8), and treatment group by visit interaction as independent factors. In this analysis, data from all post-baseline visits will be included with no imputation for missing data.

The second sensitivity analysis will use the model based multiple imputation method to impute missing data for the dichotomized IGA data. The multiple imputation will involve 3 principal tasks:

1. Missing values will be filled in 5 times to generate 5 complete data sets. The imputation model used logistic regression with factors of treatment group and analysis center (i.e., the imputation model will be the same as the analysis model).

Syntax:

```
proc mi data=datain out=dataout seed=&seed. nimpute=5 <options>;  
  class trtpn sitegr1 diiga;  
  var trtpn sitegr1 diiga;  
  monotone logistic (sitegr1=trtpn);  
  monotone logistic (diiga=trtpn sitegr1);  
run;
```

2. Each complete data set will be analyzed with a logistic regression a factors of treatment group and analysis center.
3. Results from these analyses will be combined into a single inference.

One random seed will be needed to impute IGA. The following random seed has been pre-specified by using a random number generator:

IGA Seed= 184392230

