9. DETERMINATION OF SAMPLE SIZE

The following power calculations are based on the observed Week 12 results of the Phase 2 study, SGT-EBP01-09. This study was a three-arm trial including E-BPO cream, 1% and 5%, and vehicle in the treatment of rosacea. Estimates from the E-BPO cream, 5% arm were used in the power assessments. The anticipated randomization ratio is 2:1 for E-BPO cream, 5% and vehicle, respectively. The computations were performed with nQuery Advisor Version 7.0 using a two-sided test with a statistical significance value of 0.05.

A sample size of 86 in the E-BPO cream, 5% and 43 in the vehicle group has 95% power to detect a statistically significant difference in the proportion of patients who have at least a 2-grade reduction at Week 12 from Baseline in IGA and are clear or almost clear. The estimated percentages with a 2-grade reduction at Week 12 from Baseline in the IGA and clear or almost clear are 53.3% and 20.0% for the E-BPO cream and vehicle, respectively.

A sample size of 200 in the E-BPO cream, 5% and 100 in the vehicle group has 95% power to detect a statistically significant difference in inflammatory lesions. The estimated absolute change from Baseline in treatment means were -14.1 and -7.4 for E-BPO cream and vehicle, respectively, with a standard deviation (SD) of 6.70 and 17.24, respectively.

The sample sizes above will be increased to give a planned enrollment of 234 in the E-BPO cream, 5% group and 117 in the vehicle group since the Phase 3 trial is expected to enroll patients who are as a group more severe than those of the Phase 2 trial. This is a consequence of some changes in the inclusion criteria.

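### The second sensitivity imputation drops all Week 2-8 data, so it is in effect a complete-case analysis and cannot test the ITT co-primary results against informative drop-out

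*SAP*

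**What the plan says.** The primary ITT imputation (SAP 8.1.5.1 and 8.1.5.2) is MCMC, run separately by arm, on baseline and Weeks 2, 4, 8 and 12. SAP 8.1 then announces that "a model-based multiple imputation process will be used as a sensitivity analysis to the MCMC imputation".

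That second analysis is specified in SAP 8.7.2:

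- **IGA (8.7.2.2):** the dichotomised outcome is imputed by "monotone logistic (diiga=trtpn sitegr1", that is, from treatment and analysis center. Baseline IGA and earlier visits are not in the variable list.
- **Lesion count (8.7.2.1):** Week 12 is imputed by "monotone reg (week12=trtpn baseline sitegr1", that is, from treatment, baseline count and analysis center. Earlier visits are again absent.

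Both sections say that the imputation model is deliberately the same as the analysis model. The protocol (19.4.8) says so too.

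Three other provisions bear on missing data:

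- The first sensitivity analyses in SAP 8.7.2 are a repeated-measures ANCOVA for lesions and a GEE model for IGA. Both use observed post-baseline visits without imputation.
- SAP 8.1.5 uses LOCF for the PP population.
- SAP 8.1.5 also sets patients who stop for a treatment-related AE or documented lack of effect back to their Baseline value.

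**The concern.** A sensitivity analysis of a multiple imputation is useful if it relaxes or shifts the assumption that the primary analysis makes. The primary imputation assumes that, given arm, baseline and the earlier visits, missing Week 12 values behave like observed ones. The second imputation removes the earlier visits. It then has to assume that drop-out is unrelated to the patient's course on treatment, which is stronger and less plausible.

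Early-termination data make this concrete. Under SAP 8.1.3, an exit assessment on Days 8 to 70 is mapped to Week 2, 4 or 8. A patient who leaves while still moderate or severe thus contributes a recorded failure that this model ignores.

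What is at stake is interpretation. If the second analysis agrees with the primary one, a reader may take that as evidence that the ITT co-primary results withstand informative drop-out. It is not such evidence, and nothing else planned for ITT supplies it.

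**Working it through.** **1. The plan's own figure.** SAP section 9 gives success rates ("clear or almost clear are 53.3% and 20.0% for the E-BPO cream and vehicle, respectively"), 2:1 allocation, a two-sided 0.05 test, and states: "A sample size of 86 in the E-BPO cream, 5% and 43 in the vehicle group has 95% power".

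With k = 2, difference d = 0.533 − 0.200 = 0.333 and mean rate (2×0.533 + 0.200)/3 = 0.422, the vehicle n without correction is

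[1.96·√(1.5×0.422×0.578) + 1.645·√(0.533×0.467/2 + 0.2×0.8)]² / 0.333² = 38.4, rounded up to 39.

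With continuity correction, (38.4/4)·[1 + √(1 + 6/(38.4×2×0.333))]² = 42.8, rounded up to 43 vehicle and 86 active. The stated size reproduces and is not in dispute. At the planned 234/117, power for IGA exceeds 99.9%.

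**2. What the second imputation does at the planned rates.** Neither document states a drop-out rate, so 5% to 20% is assumed. Imputed successes are missing n × 0.533 (active) and missing n × 0.20 (vehicle), with center averaged out.

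| Missing | Missing n, active / vehicle | Imputed successes, active / vehicle | Difference, second imputation | Difference, all missing fail | Difference, missing active fail and missing vehicle succeed |
|---|---|---|---|---|---|
| 5% | 12 / 6 | 6.4 / 1.2 | 33.3 | 31.6 | 26.5 |
| 10% | 23 / 12 | 12.3 / 2.4 | 33.3 | 30.1 | 19.9 |
| 15% | 35 / 18 | 18.7 / 3.6 | 33.3 | 28.4 | 13.0 |
| 20% | 47 / 23 | 25.1 / 4.6 | 33.3 | 26.5 | 6.9 |

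Example at 15%, last column: 0.533×199/234 = 45.3%; (0.20×99 + 18)/117 = 32.3%; difference 13.0 points.

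The second imputation returns 33.3 points however many patients are missing. A simple pooled z-test on the last column gives 13.0/5.57 = 2.34 at 15% and 6.9/5.55 = 1.24 at 20%, where the standard error in points is 100·√[p(1−p)(1/234 + 1/117)] with p = 0.410 and 0.403. That column is an extreme bound, not a forecast.

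**3. Size and direction of the bias.** The simulation ran 400 trials per scenario at 234/117. It assumed Week 8 success of 43% / 16%, Week 12 success of 53.3% / 20.0%, a latent Week 8 to Week 12 correlation of 0.7, 2% drop-out after Week 8 success, and the rates below after Week 8 failure. Center was not modelled.

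| Drop-out after Week 8 failure, active / vehicle | True difference | Complete cases | Imputed on arm only | Imputed on arm and Week 8 | Shift, arm only |
|---|---|---|---|---|---|
| 15% / 15% | 33.2 | 33.9 | 33.9 | 33.2 | +0.7 |
| 25% / 25% | 33.5 | 34.6 | 34.5 | 33.3 | +1.0 |
| 35% / 15% | 33.3 | 37.2 | 37.1 | 33.3 | +3.8 |
| 15% / 35% | 33.6 | 32.3 | 32.2 | 33.6 | −1.4 |

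- Arm-only imputation matches complete cases within 0.1 point.
- The leavers' true success rate is (true rate − rate with all missing counted as failures) / fraction missing. In the 25% / 25% row this is (0.534 − 0.480)/0.151 = 36% for active and (0.199 − 0.172)/0.212 = 13% for vehicle. They are imputed at 56.5% and 21.9%.
- Each arm's rate is overstated, by about 1 to 5 points. The difference moves by (fraction missing × excess) in active minus the same product in vehicle, so its sign depends on which arm loses more failing patients.
- Adding Week 8 status recovers the true difference within 0.2 point.

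**4. Whether another planned ITT analysis fills the gap.** The repeated-measures ANCOVA and GEE use earlier visits but apply no departure from their own missing-data assumptions. LOCF is confined to PP, and SAP 8.4.4 otherwise requires Week 12 attendance for PP, so little is left for LOCF to fill at Week 12. The Baseline-value rule is worded for PP in both 8.1.5 and 8.4.4, yet 8.1.5 times it after all subjects have been through the imputation. Its reach to ITT cannot be settled from the text.

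**The case against.** The strongest reply is that SAP 8.1 presents this analysis only as a check on the MCMC imputation. It replaces a normal model on IGA grades with rounding by a logistic model on the binary outcome, and matching the analysis model is a declared choice. This stands: the analysis does probe the form of the imputation, and reading it as unable to check anything about the primary result would go too far. It is uninformative about informative drop-out specifically.

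A reader might also infer that no departure from missing at random is considered anywhere. The documents do not support that. Setting treatment-failure leavers to Baseline is such a departure, and LOCF is not missing-at-random imputation either. Both are written for the supportive PP population, which limits them but does not erase them. If the Baseline rule does extend to ITT, lack-of-effect leavers are failures there and not average-rate imputations.

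Some leavers will not be imputed at all. Sites are asked to obtain Week 12 assessments at withdrawal (protocol 13.2), and an exit on Days 71 to 98 maps to Week 12.

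Finally, the shift is small against 33.3 points, and the decision rests on the primary imputation. That is correct and limits the weight of the point.

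**Conclusion.** The point holds in limited form. The second imputation discards Weeks 2-8, and for IGA also baseline, and reproduces the complete-case result apart from imputation noise. For lesions this equivalence is exact in principle for the unranked ANCOVA and approximate if the ranked analysis is used. Agreement with the primary result therefore cannot support robustness of the ITT co-primary results to informative drop-out, and no planned ITT delta, tipping-point or missing-as-failure analysis does so instead.

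The tempting further step, that this favours the active arm or puts the primary conclusion in doubt, is not supported. The illustrative shift runs from −1.4 to +3.8 points and changes sign with the drop-out pattern. Even the extreme bound stays significant at 15% missing and loses significance only at 20%. These figures rest on assumed drop-out rates, an assumed Week 8 success rate and an assumed correlation; none is in the documents. This is an inexpensive improvement to the sensitivity set, not a flaw in the primary analysis.

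**What to change.** In SAP 8.7.2:

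1. Impute Week 12 from treatment, analysis center, baseline and Weeks 2, 4 and 8. Use fully conditional specification, because the MONOTONE statements cannot take intermittently missed visits, which the plan expects (PP tolerates one missed visit before Week 12). Impute the IGA grade with an ordinal logistic model, then dichotomise.
2. Add a pre-specified ITT tipping-point analysis. Worsen the imputed active-arm Week 12 values in fixed steps until p exceeds 0.05, and report that point. For lesions, add the step to the imputed count before any ranking. For IGA, shift on the log-odds scale. Fix the step sizes before unblinding.

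In SAP 8.1.5, state whether the rule setting related-AE and lack-of-effect leavers to Baseline applies to ITT or to PP only.

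The cost is some extra programming and one more sensitivity table. No new data are needed and the primary analysis is unchanged. With the earlier visits added, the second imputation will share most of its variables with the primary one, so the tipping-point analysis is what tests the assumption. The SAP allows updates until the blind is broken.
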